### 8.2.2.2 Derivation of seizure frequency related variables

The following variables will be defined for each visit and Month 12 /Withdrawal using the 28-day Baseline and 28-day post-Baseline seizure frequency variables described in [Section 8.2.2.1](#).

- Absolute reduction in POS frequency defined as:  
$$28\text{-day Baseline} - 28\text{-day post-Baseline seizure frequency}$$
- Percent reduction in POS frequency defined as:  
$$\frac{28\text{-day Baseline} - 28\text{-day post-Baseline seizure frequency}}{28\text{-day Baseline}} \times 100$$
- Patients with 0 POS at Baseline will be excluded from the analysis of percent reduction and response ( $\geq 50\%$ ).
- Response (Yes, No) where Yes is  $\geq 50\%$  reduction in POS frequency calculated as described above and No otherwise.
- Seizure freedom (Yes, No) will be defined using 2 methods as shown in [Table 8-1](#). The first method considers patients who withdraw prior to their 1st seizure as Not seizure free. The 2nd is a less conservative method which considers patients who withdraw prior to their 1st seizure as missing. Visit 4 (Month 12/Withdrawal) will not be summarized for seizure freedom.

Table 8–1: Derivation of seizure freedom		
Patient Classification at Visit (patients are assigned to the first category they fall into)	Seizure freedom – Discontinuations counted as not seizure free	Seizure freedom – Discontinuations counted as missing
0. Patients had a seizure before 1st BRV dose	Missing	Missing
1. Patient had a seizure on or after 1st BRV dose and on or before the visit date derived using the following conditions. First_seizure_date = Date of first seizure or if date of first seizure is missing but patient has seizures recorded at a visit, then assign first_seizure_date as the date of the visit prior to the earliest visit with seizures recorded a) Visit date present and First_seizure_date is on or after 1st BRV and on or before the Visit date b) Visit date is missing (either due to patient ongoing in study or visit missed) and First_seizure_date is on or after 1st BRV and on or before the visits target day [a])	No	No
2. Patient discontinued BRV or terminated the study prior to the visit’s target day [a]	No	Missing
3. Patient had missing seizure data at the visit (or missed the visit) but had not discontinued BRV or terminated the study prior to the visit’s target day [a]. Note: If a patient is ongoing in the study and had not got to the visit yet, they are treated in the same way as having missed visit.	Missing	Missing
4. Patient met none of the above classifications and patient has the visit present	Yes	Yes

[a] The target day for each visit is: Visit 2 (Month 3) = Day 90, Visit 3 (Month 6) = Day 180, and Visit 4 (Month 12) = Day 330. For Month 12 assessments, seizure freedom will be analyzed for completers only. Therefore assign missing to all patients who withdraw for the Month 12 analyses.

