## **8 SELECTION AND WITHDRAWAL OF PATIENTS**

### **8.1 Selection criteria**

Before any data are collected for any patient in this NIS, written data consent will be properly executed and documented.

The following selection criteria must be followed for patients entering the NIS:

1. Patient has never been treated with BRV prior to inclusion in this NIS.
2. The decision by the treating physician to prescribe BRV is made independently of the participation in the NIS.
3. A Patient Data Consent form is signed and dated by the patient or by the parent(s) or legal representative.
4. Patient is a male or female  $\geq 16$  years of age.
5. Patient has a clinical diagnosis of epilepsy with POS with or without secondary generalization.
6. Patient meets the criteria for treatment with BRV as adjunctive therapy according to the current SmPC in Europe.
7. Patient uses an epilepsy/seizure diary.

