#### **4.8 Examination of subgroups**

- Age at Visit 1 (<65 and ≥65 years).
- Time since first diagnosis of epilepsy (0-<1 years, 1-<5 years, 5-10 years, >10 years): Defined in [Section 6.2](#)
- Number of AEDs at study entry (0, 1, 2, 3 and >3 AEDs) : Defined in [Section 6.4](#)
- Number of Historical AEDs (0 or 1 or 2 or 3, 4 or 5 or 6, >6): Defined in [Section 6.4](#)
- Historical Levetiracetam (LEV) use (Yes, No): Defined in [Section 6.4](#)
- Number of Lifetime AEDs (0 or 1 or 2 or 3, 4 or 5 or 6, >6): Defined in [Section 6.4](#)
- 28-day Baseline all seizures frequency (≤5, >5-10, >10): Defined in [Section 8.2.2.1](#)

The number of patients in the subgroup categories listed above will be examined at the DEM meeting to ensure sufficient patients exist in each category for statistical analysis of the primary and secondary variables by subgroup to offer meaningful analyses. For example, if it is deemed that there are an insufficient number of patients in the ≥65 years age at Visit 1 category, then the age at Visit 1 categories may be amended to use <60 and ≥60 years instead.

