### 6.2 Other Baseline disease characteristics

The following Baseline disease characteristics will be summarized:

- History of Epilepsy
  - Time since first diagnosis of epilepsy (years)  
(Date of Visit 1 – Date of first diagnosis of epilepsy) / 365.25  
Note that as the day of first diagnosis is not collected in the CRF it will be imputed per the rules outlined in [Section 4.2.2](#). If the time since first diagnosis is greater than the patient's age due to the application of imputation rules, then time since first diagnosis will be set to equal the patient's age. If the time since first diagnosis is less than or equal to 0 due to the imputation rules, then time since first diagnosis will be set to 0.
  - Time since first diagnosis of epilepsy (0-<1 year, 1-<5 years, 5-10 years, and >10 years)
  - Age at time of first diagnosis of epilepsy (years)  
Age – Time since first diagnosis of epilepsy
  - Percent of life with epilepsy  
 $100 \times \text{Time since first diagnosis of epilepsy (years)} / \text{Age}$
  - Reason for initiation of BRV (Behavioral side effects to current AED, Other intolerance to current AED, Lack of efficacy of current treatment, Administer therapeutic dose without titration, or Other): as recorded in the Initiation of Medication CRF form
- Baseline seizure frequency as described in [Section 8.2.2.1](#) summarized as a continuous variable and in the following categories (≤5, >5-10, and >10 seizures per 28-days)

- 28-day Baseline all seizure frequency
- 28-day Baseline POS frequency
- 28-day Baseline POS with secondary generalization frequency
- Epilepsy etiology and seizure classification
  - Whether the etiology of epilepsy is known and the type of etiology as recorded in the Etiology of Epilepsy CRF form
  - Seizure history profile based on the 1981 International League Against Epilepsy (ILAE) Classification. Any POS (I) and each seizure sub type (IA [also broken down into IA1, IA2, IA3, IA4], IB and IC) as recorded in the ILAE Seizure Classification History CRF page

The following by-patient listings will be provided

- History and etiology of epilepsy (including time to first diagnosis, age at first diagnosis, percent of life with epilepsy, etiology, ILAE Seizure classification and reason for BRV initiation)
- Baseline seizure count (including number of all seizures, POS and POS with secondary generalization seizures)

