### **8.2.2 Seizure frequency related variables**

#### **8.2.2.1 Initial processing of diary data**

The number of POS since the last visit will be reported at each visit and Month 12/ Withdrawal. The 28-day post-Baseline seizure frequency for POS will be calculated as:

---

$$\frac{\text{Number of POS recorded at visit}}{\text{(Date of visit – Date of previous visit)}} \times 28$$

(Date of visit – Date of previous visit)

Partial-onset seizures frequency will only be calculated at visits attended and with seizure data recorded. For seizure frequency summaries, data recorded at Visit 4 (Month 12/Withdrawal) visit will be mapped to the appropriate scheduled visits as described in [Section 3.2.2](#). No mapping will be performed for Seizure freedom as the derivation is date based rather than visit based.

Twenty eight-day Baseline POS frequency (28-day Baseline) will be calculated using the Historical Seizure Count CRF page, as the number of POS recorded during the 3 months prior to first BRV administration / 3. For all seizures and POS with secondary generalization, the 28-day Baseline will be calculated using the same method of dividing the number recorded during the 3 months prior to first BRV administration by 3.

If Visit 4 data are missing, then the Visit 4 (Month 12) and Visit 4 (Month 12/Withdrawal) seizure rates will be missing. Visit 4 (Month 12) and Visit 4 (Month 12/Withdrawal) will be derived according to [Section 3.2.2](#).

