### 8.2.2.3 Analysis of seizure frequency related variables

The following tables will be produced on the FAS and all tables except the by subgroup tables will be repeated on the modified FAS:

- Descriptive statistics of the POS frequency at Visit 1 (Baseline), Visit 2 (Month 3), Visit 3 (Month 6), Visit 4 (Month 12), and Visit 4 (Month 12/Withdrawal)
- Descriptive statistics of the absolute reduction in POS frequency (seizures per 28 days) from Visit 1 (Baseline) to Visit 2 (Month 3), Visit 3 (Month 6), Visit 4 (Month 12), and Visit 4 (Month 12/Withdrawal)

- Descriptive statistics of the absolute reduction in POS frequency (seizures per 28 days) by subgroups described in [Section 4.8](#), from Visit 1 (Baseline) to Visit 2 (Month 3), Visit 3 (Month 6), Visit 4 (Month 12), and Visit 4 (Month 12/Withdrawal).
- Descriptive statistics of the percent reduction in POS frequency (seizures per 28 days) from Visit 1 (Baseline) to Visit 2 (Month 3), Visit 3 (Month 6), Visit 4 (Month 12), and Visit 4 (Month 12/Withdrawal)
- Number and percentage of responders ( $\geq 50\%$  reduction) at Visit 2 (Month 3), Visit 3 (Month 6), Visit 4 (Month 12), and Visit 4 (Month 12/Withdrawal)
- A sensitivity analysis of the responder analysis will be performed on two subsets of the FAS and modified FAS as defined in [Section 4.6](#) (patients who completed the study and patients who discontinued the study due to lack of efficacy).
- Number and percentage with seizure freedom (using the 2 methods described in [Table 8–1](#)) at Visit 2 (Month 3), Visit 3 (Month 6), and Visit 4 (Month 12)
- A sensitivity analysis of the seizure freedom analysis will be performed on two subsets of the FAS and modified FAS as defined in [Section 4.6](#) (patients who completed the study and patients who discontinued the study due to lack of efficacy).
- Number and percentage with seizure freedom (using discontinuations counted as seizure freedom = no) by subgroups described in [Section 4.8](#), at Visit 2 (Month 3), Visit 3 (Month 6), and Visit 4 (Month 12)

The following by-patient listings of seizure data will be produced on the All Subjects Documented set:

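### Seizure freedom and time to first seizure pool patients with no seizures in the 3-month Baseline with patients who had them, and no planned summary separates the two

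*SAP*

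**What the plan says.** **Baseline.** SAP 8.2.2.1 computes the 28-day Baseline POS frequency "as the number of POS recorded during the 3 months prior to first BRV administration / 3", and treats the all-seizure count in the same way.

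**Percent reduction and response.** SAP 8.2.2.2: "Patients with 0 POS at Baseline will be excluded from the analysis of percent reduction and response".

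**Seizure freedom.** Table 8-1 in the same section assigns each patient to the first category that fits. The first, "0. Patients had a seizure before 1st BRV dose", gives Missing under both methods and states no look-back period. The last, "4. Patient met none of the above classifications and patient has the visit present", gives Yes under both methods and sets no condition on Baseline seizures. The table footnote restricts Month 12 to completers. SAP 8.2.2.3 then tabulates, on the FAS and modified FAS, "Number and percentage with seizure freedom (using the 2 methods described in" Table 8-1.

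**Time to first seizure.** SAP 8.2.3 runs the Kaplan-Meier analysis on the FAS and modified FAS, with no Baseline condition.

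**Who can enter.** Protocol 8.1 asks for a diagnosis and sets no minimum count: "Patient has a clinical diagnosis of epilepsy with POS with or without secondary generalization". The FAS (SAP 3.5) removes only patients with previous BRV use. Reasons for starting BRV in SAP 6.2 include "Behavioral side effects to current AED" and other intolerance, as well as lack of efficacy.

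**Subgroups.** SAP 4.8 uses "28-day Baseline all seizures frequency (≤5, >5-10, >10" as the Baseline-frequency bands.

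**The concern.** A patient who changes treatment for tolerability may have had no seizures in the preceding 3 months. If that patient has none on BRV, the result is continued absence of seizures. In a patient who was having seizures, the same result is gained control. Both are worth describing, but they are different findings, and the secondary objective concerns control of seizures on BRV.

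Pooling raises the seizure-freedom rate, and lengthens time to first seizure, whenever zero-Baseline patients do better than the others. It also places the responder and seizure-freedom percentages on different patients: someone can be seizure free yet not eligible to be a responder. A reader who compares the two columns, or compares the freedom rate with the Phase 3 studies (which, per Protocol section 1, required at least 8 POS during Baseline), would see nothing in the tables to show this.

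**Working it through.** **1. One patient traced through the derivations.** Take a patient with 0 seizures in the 3-month Baseline, none on BRV, and all visits present.

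| Analysis | Treatment of this patient |
|---|---|
| Percent reduction, response | Excluded |
| Absolute reduction | Kept; can contribute only zero or a negative value |
| Seizure freedom, both methods | Yes |
| Time to first seizure | Kept; censored at the last visit |

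Eligibility and the FAS definition do not remove this patient. The sensitivity subsets in SAP 4.6 (completers; discontinued for lack of efficacy) do not isolate the group.

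**2. The lowest band.** The Baseline rate is the 3-month count divided by 3, so ≤5 per 28 days covers counts from 0 to 5 × 3 = 15.

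**3. The plan's own figure.** SAP 2.4 sizes the FAS for retention: (1.959964/0.05)² × 0.25 = 384.15, rounded up to 385, which reproduces. No figure in the documents concerns seizure freedom or the number of zero-Baseline patients, so what follows illustrates the mechanism and does not estimate its size.

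**4. Seizure freedom.** Let f be the zero-Baseline share of evaluable patients, p0 the freedom rate in them and p1 the rate in the rest. None is in the documents. Assumed ranges are f 5% to 30%, p0 50% to 90%, p1 5% to 15%. Category 0 is read narrowly, as a seizure between Visit 1 and the first dose.

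- Pooled rate = f·p0 + (1 − f)·p1
- Excess over p1 = f·(p0 − p1)
- Share of the seizure free who had no Baseline seizures = f·p0 / [f·p0 + (1 − f)·p1]

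**5. Time to first seizure.** This assumes exponential times with a median of 20 days in patients with Baseline seizures and 365 days in zero-Baseline patients. The pooled curve is S(t) = f·2^(−t/365) + (1 − f)·2^(−t/20), solved for S = 0.50 and S = 0.25.

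The table uses p0 = 70% and p1 = 10%, and a FAS of 530 × 0.9 = 477 (an assumption taken from the plan's 10% allowance). Denominators are before missing data.

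| f | Zero-Baseline patients | Response denominator | Pooled freedom (10% in the rest) | Seizure free with no Baseline seizures | Pooled median, days (20 in the rest) | 75% with a seizure by, days (40 in the rest) |
|---|---|---|---|---|---|---|
| 5% | 24 | 453 | 13.0% | 27% | 21.4 | 44 |
| 10% | 48 | 429 | 16.0% | 44% | 23.1 | 50 |
| 20% | 95 | 382 | 22.0% | 64% | 27.3 | 69 |
| 30% | 143 | 334 | 28.0% | 75% | 33.6 | 120 |

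Example at f = 20%: 0.20 × 0.70 + 0.80 × 0.10 = 0.14 + 0.08 = 22%.

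**6. Extremes of the assumed ranges.**

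- Lowest pooled rate: 0.05 × 0.50 + 0.95 × 0.05 = 7.25%. Highest: 0.30 × 0.90 + 0.70 × 0.15 = 37.5%. Part of this spread comes from p1 itself.
- The excess over p1 isolates the pooling: from 0.05 × (0.50 − 0.15) = 1.75 points to 0.30 × (0.90 − 0.05) = 25.5 points.
- The share of the seizure free with no Baseline seizures runs from 0.025/0.1675 = 15% to 0.27/0.305 = 89%.

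**The case against.** **Table 8-1 does contain a rule on earlier seizures.** Category 0 is applied first and has no window. Read literally, it sets every patient with Baseline seizures to Missing; nothing is then pooled and the mixture formula does not apply to seizure freedom. This stands as a reason to settle category 0 first. It does not rescue the analysis, because the literal reading leaves only patients without earlier seizures able to count as seizure free. The narrow reading is more plausible: Protocol Table 17-1 allows the first dose to fall after Visit 1.

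**The exclusion from response is arithmetic.** Percent reduction divides by the Baseline rate, so zero must be excluded. A reader might infer from the rule that the sponsor expects many such patients; the documents do not support that. The rule shows only that a zero Baseline is provided for. The difference in denominators is unavoidable, but it can still be shown.

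**Three months without a seizure is not established seizure freedom.** This stands. A patient averaging 2 seizures a year (assumed, Poisson) has an exp(−0.5) = 61% chance of none in 3 months, but only exp(−2 × 330/365) = 16% of none over 330 days. Twelve months without seizures in such a patient is not simply a state carried over from before BRV.

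**The study is descriptive and single-arm, and remaining seizure free is a form of control.** Also true, so the all-FAS result is legitimate and should stay.

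**The data are partly visible already.** Seizure freedom is tabulated by Baseline band, reason for initiation is summarised, and by-patient listings allow the split. SAP 4.8 also lets the data evaluation meeting revise categories, but on grounds of small numbers. No planned summary isolates zero, and time to first seizure has no subgroups.

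**Conclusion.** The gap is real. Zero-Baseline patients leave the response analysis but can count as seizure free (completers only at Month 12) and lengthen time to first seizure, and no planned summary shows them apart. Statements about seizure control would rest on a mixture whose composition is not reported.

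The direction is upward whenever p0 exceeds p1. The amount cannot be derived from the documents. The excess of 1.75 to 25.5 points, and the shift in the median from 20 days to between 21.4 and 33.6 days, depend entirely on the assumed shares, rates and medians and on the narrow reading of category 0. In absolute reduction these patients pull the mean the other way.

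A reader might go further and conclude that most patients reported as seizure free were already so before BRV. The documents do not support this: the share runs from 15% to 89% within the assumed ranges, and a zero count over 3 months does not establish prior freedom.

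The primary variable (retention) and the sample size are untouched. This is a worthwhile correction to the secondary analysis and does not invalidate the plan.

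**What to change.** 1. **Table 8-1.** Give category 0 an explicit window, for example from Visit 1 to before the first BRV dose. The other changes cannot be programmed reliably until this is settled.
2. **SAP 8.2.2.3 and 8.2.3.** Keep the all-FAS results. Add seizure freedom and time to first seizure separately for patients with ≥1 and with 0 seizures in the 3-month Baseline, each with its denominator. Use the all-seizure count from the Historical Seizure Count page, because Table 8-1 and 8.2.3 refer to seizures without limiting them to POS.
3. **SAP 4.8.** Split the ≤5 band into 0 and >0 to 5.
4. **Reporting.** Base statements on gained seizure control on the ≥1 group. Label the other group 'no seizures in the 3-month Baseline', not 'maintained seizure freedom'.

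The cost is SAP wording and a few extra table rows from data already collected. The seizure-freedom figure used for statements on control may be less favourable.

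### Two date rules in SAP Table 8-1 miscode seizure freedom when the first seizure is undated: no first-dose floor, and an inclusive date test that overrules a recorded zero

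*SAP*

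**What the plan says.** Seizure freedom at 3, 6 and 12 months is a secondary variable (SAP 2.2.2), tabulated overall and by subgroup (SAP 8.2.2.3). Table 8-1 in SAP 8.2.2.2 derives it from ordered rows, and "patients are assigned to the first category they fall into".

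- Row 0, "Patients had a seizure before 1st BRV dose", gives Missing under both methods at every visit.
- Row 1 gives No. For an undated first seizure the instruction is to "assign first_seizure_date as the date of the visit prior to the earliest visit with seizures recorded". Where the visit took place, row 1a requires that "First_seizure_date is on or after 1st BRV and on or before the Visit date".
- Row 4, "Patient met none of the above classifications and patient has the visit present", gives Yes.
- Footnote [a], on Month 12: "Therefore assign missing to all patients who withdraw for the Month 12 analyses".

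The counts cover the interval between visits: "The number of POS since the last visit will be reported at each visit" (SAP 8.2.2.1; SAP 4.2.1 is to the same effect).

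For time to first seizure, Table 8-2 (SAP 8.2.3) handles the same undated seizures differently. When the event would be placed at Visit 1, its note moves the date to the first BRV dose if that is later. The stated aims are to avoid negative times and under-reporting of seizures.

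**The concern.** A missing seizure date should make the timing uncertain. It should not reverse what the counts show. Table 8-1 allows that in two ways.

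**A. No first-dose floor.** An undated seizure reported at the first post-Baseline visit attended is dated to Visit 1. If first BRV is after Visit 1, that date precedes first dose and row 1 cannot apply. The patient ends as Missing or as Yes, depending on how row 0 is read, while Table 8-2 counts an event at first dose.

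**B. Inclusive test.** Undated seizures first reported after a visit with a recorded zero are dated to that zero visit. Row 1a accepts a date equal to the visit date, so the visit is coded No although no seizure was counted up to then.

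A related point is precedence. Because row 0 is tested before row 1, a seizure dated between Visit 1 and first dose keeps the patient Missing at Months 6 and 12, even when later intervals lying wholly on BRV contain seizures.

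At stake are the reported percentages for one secondary variable and their subgroup versions, where each patient weighs more.

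**Working it through.** The plan states no figure for this point, so the check applies the rules to test patients.

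**Inputs.** Rows 0 to 4 of Table 8-1; the nine undated-seizure patterns of Table 8-2; completers on BRV with visits at days 91, 182 and 364 (assumed); first dose on the day of Visit 1 or 5 days later (assumed).

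**Can first dose follow Visit 1?** Nominally not: Protocol section 5 and SAP 2.3 call Visit 1 the first day of BRV. But Protocol Table 17-1 footnote a makes same-day dosing conditional, and the Table 8-2 note provides for a later first dose.

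**Results at Months 3/6/12.** M = attended without seizure data; - = visit missed.

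| Counts at Visits 2, 3, 4 (undated) | Table 8-1, no gap | Table 8-1, 5-day gap | With floor and strict test |
|---|---|---|---|
| >0, >0, >0 | No/No/No | Missing at all three, or Yes/Yes/Yes | No/No/No |
| -, >0, >0 | No/No/No | Missing at all three, or Missing/Yes/Yes | No/No/No |
| 0, >0, >0 | No/No/No | same as no gap | Yes/No/No |
| 0, 0, >0 | Yes/No/No | same as no gap | Yes/Yes/No |
| 0, -, >0 | No/No/No | same as no gap | Yes/No/No |

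In the gap column, the first result applies if row 0 reads the imputed date and the second if it needs a recorded date. So 3 of the 9 patterns show fault B with no gap, and 2 more show fault A with a gap. If the 0, >0, >0 patient's first seizure is instead dated to day 120, Month 3 is Yes. The missing date alone reverses that code.

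The other 4 patterns (M,M,>0; M,>0; M,-,>0; -,M,>0) contain an attended visit without seizure data. They show neither fault. The strict test does touch them: at the attended visit without data that the seizure is dated to, the code moves from No (row 1a) to Missing (row 3).

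**Per-patient size.** 1/385 = 0.26 points; 1/530 = 0.19 points (SAP 2.4 figures). A fault B case lowers Yes by this amount at one visit. A fault A case read as Yes raises it at each visit affected.

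**Row 0 precedence.** On denominator N, the general rule in SAP 3.1, moving a patient from No to Missing lowers No by 1/N and leaves Yes unchanged. With Missing excluded, assume true Yes is 15%. Let m be the percentage of patients with a pre-dose seizure and later on-BRV seizures, and f the percentage with a pre-dose seizure who are then seizure-free. Now: Yes = (15 - f)/(100 - f - m). If the first group is recoded No and the second stays Missing: Yes = (15 - f)/(100 - f).

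| m, f | Now (error) | After recoding (error) |
|---|---|---|
| 1, 0.1 | 15.07% (+0.07) | 14.91% (-0.09) |
| 5, 0.5 | 15.34% (+0.34) | 14.57% (-0.43) |
| 10, 1 | 15.73% (+0.73) | 14.14% (-0.86) |
| 4.25, 0.75 | 15.00% (0.00) | 14.36% (-0.64) |

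Recoding therefore makes the Missing-excluded percentage worse in these scenarios, because only patients with seizures leave the Missing group.

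**The case against.** The preconditions are narrow. Fault A needs a first dose after Visit 1, off the nominal schedule. Both faults need an undated first seizure, although seizure dates are collected (Protocol Table 17-1) and the physician reviews the diary and interviews the patient about gaps (Protocol section 11). The pattern counts are logical cases, not expected patients. SAP 8.2.3 also calls its handling of undated seizures conservative, and fault B uses the same imputed date. All of this stands, and it limits the size. It does not rescue the rules. A conservative date suits event timing but should not overrule an observed zero, and the plan already has the first-dose floor in the neighbouring table.

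A reader might infer more than the documents support:

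- *That row 0 inflates seizure freedom.* On N it leaves Yes unchanged and understates No. Inflation arises only if Missing is excluded, which is not the general rule of SAP 3.1.
- *That Missing at Month 3 contradicts the record.* The Visit 2 count starts at Visit 1, so with a later first dose it straddles that dose and Missing is defensible. For row 0 the conflict is firm only at Months 6 and 12.
- *That row 0 sweeps in the historical seizures.* Baseline for all seizures is formed by "using the same method of dividing the number recorded during the 3 months prior to first BRV administration by 3", and row 0 states no look-back limit. But that reading would set to Missing every patient with a seizure in those months, and the listing in SAP 8.2.2.3 works from the first seizure in the study. This is a wording gap, not an expected coding.
- *That row 1 must be changed because it names no seizure type.* That is a separate choice of scope; no miscoding follows from it here.

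**Conclusion.** Faults A and B follow from Table 8-1 as written, and nothing in SAP 4.2, 8.2.2 or 8.2.3 overrides them for seizure freedom. Fault B needs only an undated first seizure and can only understate seizure freedom. Fault A also needs a first dose after Visit 1. Whether it yields Missing or Yes depends on an ambiguity in row 0, and Yes is only one of the two readings.

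The row 0 order is a lesser, separate matter: on N it understates No at Months 6 and 12 and leaves Yes alone. A wholesale reordering of the rows is not supported, because it ties missingness to outcome.

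The documents give no frequency of undated first seizures or delayed first doses, so overall size and net direction are unknown. Each affected patient moves a percentage by 0.26 points at N = 385 or 0.19 at N = 530. The analysis is descriptive and the primary retention variable is unaffected. The plan should be corrected, but its main result does not depend on it.

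**What to change.** 1. In Table 8-1 row 1, date an undated first seizure that would fall at Visit 1 to the later of Visit 1 and first BRV, as Table 8-2 does. Cost: an undated seizure in an interval straddling first dose is coded No although it may have been pre-dose. That is conservative and agrees with Table 8-2.
2. In row 1a, for imputed dates only, require the first-seizure date to be strictly before the visit date, so that a recorded zero stands. Table 8-2 needs no change. Side effect: the four patterns with an attended visit lacking seizure data move from No to Missing at one visit. If that is unwanted, apply the strict test only at visits with a recorded zero.
3. State that row 0 means a seizure dated between Visit 1 and first BRV.
4. If patients caught by row 0 with later on-BRV seizures are to be recoded No, do so only in the table based on N, and say that a Missing-excluded percentage would then depend on outcome.

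The work is an edit to one SAP table and its derivation program. No new data are needed.

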#### **4.2.1 Seizure diary**

Seizure data will be recorded at each visit as described in [Section 8.2.2.1](#).

The treating physician will use the patient diaries to calculate the number of seizures since the previous visit and will enter this information into the CRF. Hence, if a patient misses a visit, as long as they have diaries available when they attend the next visit, then the seizure information can still be utilized.

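### Table 8-1 lets later diary data turn a missed Visit 2 or 3 into a seizure-freedom failure but never a success, so the Month 3 and Month 6 rates lean low

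*SAP*

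**What the plan says.** SAP 8.2.2.2, Table 8-1, derives seizure freedom in two versions that differ only in how discontinuations are counted. The rows are ordered: "patients are assigned to the first category they fall into". For a patient who missed Visit 2 or Visit 3 the relevant rows are:

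- **Row 1b:** "Visit date is missing (either due to patient ongoing in study or visit missed) and First_seizure_date is on or after 1st BRV", and also no later than the target day: *No* in both versions. If seizures are recorded without a date, the rule is to "assign first_seizure_date as the date of the visit prior to the earliest visit with seizures recorded".
- **Row 2:** "Patient discontinued BRV or terminated the study prior to the" target day: *No* in one version, *Missing* in the other.
- **Row 3:** "Patient had missing seizure data at the visit (or missed the visit) but had not discontinued BRV or terminated the study prior to" the target day: *Missing* in both.
- **Row 4:** "Patient met none of the above classifications and patient has the visit present": *Yes* in both.

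The target days are Day 90 (Month 3) and Day 180 (Month 6).

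Three other places bear on the same patient. SAP 4.2.1 says of a patient who misses a visit that, "as long as they have diaries available when they attend the next visit, then the seizure information can still be utilized". SAP 8.2.2.1 explains why withdrawal visits are not mapped for this variable: "No mapping will be performed for Seizure freedom as the derivation is date based rather than visit based". SAP 8.2.3, item 3, censors a patient with no recorded seizures who is still on BRV at the last visit.

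**The concern.** A seizure date learned at a later visit is used when it makes the missed-visit patient a failure. It is discarded when it shows the patient was seizure free at the target day. Whether the result is missing therefore depends on the outcome itself.

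Seizure freedom at 3 and 6 months are named secondary variables (SAP 2.2.2) and are also tabulated by subgroup (SAP 8.2.2.3). A descriptive rate that drops documented successes while keeping documented failures will read low. Subgroups with different attendance would be affected to different degrees.

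**Working it through.** **1. Apply the table literally.** Row 0 (seizure before the first dose) is set aside. Coding rows 1a to 4 as an ordered rule and running it for a missed visit, over no seizure or a first seizure on any of Days 1 to 399, a grid of stopping days, and both target days, gives only row 1b (*No*/*No*), row 2 (*No*/*Missing*) or row 3 (*Missing*/*Missing*). *Yes* never occurs. Particular records:

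- Visit 2 missed, Visit 3 reports zero seizures, patient continues: Month 3 is *Missing*. Protocol Section 11 collects seizures since the previous study visit, so that zero covers Day 90.
- Visit 2 missed, first seizure dated Day 120: Month 3 is *Missing*, although no seizure occurred by Day 90.
- Visit 3 missed, withdrawal visit on Day 185 with zero seizures, BRV and study participation continued to at least Day 180: Month 6 is *Missing*. Under SAP 3.2.2 the same visit is mapped to Month 6 for seizure frequency (window 136 to 329). With a Baseline POS count above zero, this patient is a Month 6 responder but has no Month 6 seizure-freedom result.
- Zero seizures with the visit attended: *Yes*.

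**2. Direction.** As shares of the analysis set N, let Y be attenders scored *Yes* and x be seizure-free patients lost to row 3. Considering this rule alone, the true share is Y + x.

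- Denominator N (SAP 3.1, stated as the general rule): reported Y, which is below Y + x whenever x > 0.
- Non-missing denominator, if every missed-visit failure is scored *No*: reported Y/(1 − x). This is at most Y + x, because (Y + x)(1 − x) − Y = x(1 − Y − x) ≥ 0. Equal rates in attenders and non-attenders are not needed.

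**3. Where the second result weakens.** If Visit 2 was missed and undated seizures appear at Visit 3, Table 8-1 dates them to Visit 1. Protocol Table 17-1, footnote a, allows the first dose to come after Visit 1. The assigned date then precedes first BRV, row 1b fails and the patient becomes *Missing*. If e is the share of N escaping in this way, the non-missing rate is Y/(1 − x − e). Table 8-2 avoids the problem by using the first-dose date when that is later than Visit 1; Table 8-1 does not.

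**4. Size, under assumptions only.** The documents state no figure to reproduce. Let s be true freedom and m the share missing the visit, both assumed, with m unrelated to outcome and every missed visit covered by later data. Reported rate: s(1 − m) with N; s(1 − m)/(1 − sm) among non-missing.

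| s | m | Denominator N | Non-missing |
|---|---|---|---|
| 10% | 5% | 9.5% | 9.5% |
| 10% | 10% | 9.0% | 9.1% |
| 10% | 20% | 8.0% | 8.2% |
| 20% | 10% | 18.0% | 18.4% |
| 30% | 5% | 28.5% | 28.9% |
| 30% | 10% | 27.0% | 27.8% |
| 30% | 20% | 24.0% | 25.5% |

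If only a share b of missed visits is covered by later data, the loss this rule causes with denominator N is s·m·b. For s = 30%, m = 10%, b = 50%, that is 0.30 × 0.10 × 0.50 = 1.5 points instead of 3.0.

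For step 3, with s = 30% and m = 10%: Y = 0.27, x = 0.03, and missed-visit failures are 0.07. If half escape row 1b, the non-missing rate is 0.27/(1 − 0.03 − 0.035) = 28.9%. If all escape, it is 0.27/(1 − 0.03 − 0.07) = 30.0%, and the bias is gone.

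**The case against.** Several points can fairly be made for the plan.

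- **The diary data are used elsewhere.** SAP 4.2.1 depends on diaries being available, and the information does reach the next visit's seizure frequency, row 1b and time to first seizure. A reader might infer that 4.2.1 promises no seizure information is lost through a missed visit, so that Table 8-1 flatly contradicts it. The wording does not go that far. What stands is an inconsistency: usable information is used in one direction only.
- **A bridging estimate is planned.** The Kaplan-Meier analysis in SAP 8.2.3 gives monthly estimates that can use data beyond a missed visit, and the by-patient listing shows first-seizure and target dates. That makes the problem detectable, but the named Month 3 and Month 6 variables remain as they are. The completer and lack-of-efficacy subsets in SAP 4.6 name no other derivation.
- **It is conservative.** SAP 8.2.2.2 declares conservatism for withdrawals only. The less conservative version has the same defect, and no reason is given for missed visits.
- **The loss is visible and may be small.** With denominator N, missing patients have their own row. A reader might infer that missed visits must be common because visits follow routine practice. That does not follow: with approximate timing, a late visit can still be recorded as Visit 2.
- **Reclassification treats absentees more gently.** With a first seizure on Day 100, an attender seen on Day 120 is *No* at Month 3, while a patient who skipped Visit 2 would become *Yes*. This is a real cost, but row 1b already judges missed-visit patients at the target day.

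The study is single-arm and descriptive. Primary retention is untouched, and Month 12 seizure freedom is not affected in this way because no visit follows Visit 4.

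**Conclusion.** The asymmetry is plain on the text. For patients who miss Visit 2 or 3 and remain on BRV and in the study to the target day, later data can yield *No* or *Missing*, never *Yes*. Taken alone, this understates Month 3 and Month 6 seizure freedom, including the subgroup tables, with the SAP 3.1 denominator.

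A reader might infer that the bias is downward whichever denominator is used. The documents do not support that. Among non-missing patients it is generally downward, but it shrinks and can vanish where undated seizures are dated to a Visit 1 before first BRV.

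The size cannot be stated. It depends on the share of patients whose missed visit is covered by later seizure data, and it is zero if no visit is missed. Over the assumed ranges (true freedom 10% to 30%, missed visits 5% to 20%, all covered), the understatement is 0.5 to 6.0 points with N and 0.45 to 4.5 points among non-missing if row 1b catches every failure. These figures are illustrations, not estimates for this study. The point is worth correcting because the data exist and the rule disagrees with SAP 4.2.1, 8.2.2.1 and 8.2.3; it does not threaten the primary result.

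**What to change.** Amend Table 8-1 rows 3 and 4 together; changing row 3 alone leaves the row 4 requirement that the visit be present.

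- Where Visit 2 or 3 was missed, BRV and study participation continued to the target day, and a later attended visit (including the withdrawal visit) on or after the target day has seizure data covering the gap: *Yes* if no seizure occurred from first BRV to the target day, otherwise *No*. This is the cut-off row 1b already uses.
- Keep *Missing* where no later data cover the gap. That includes a visit attended without seizure data, since the next count starts from that visit.
- Date undated seizures to the later of the prior visit and first BRV, as Table 8-2 does.
- Correct the sentence in SAP 8.2.2.1 on the date-based derivation to match, and state the denominator of the seizure-freedom tables.

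The cost is a short SAP change and a small programming change, with no new data. The remaining drawback is that attenders are judged to their actual visit date (row 1a) and bridged patients to the target day. A footnote should say so.
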